4.3.4 DISPOSING OF CONSUMABLES

Worn lenses collected during study visits will be discarded as per University of Waterloo regulations.

4.3.5 PRODUCT ACCOUNTABILITY

Accountability logs will be kept to include the number of lenses and lens care system bottles received, dispensed, unused and returned to sponsor (where relevant). All products dispensed to participants will be recorded in individual participant logs in the study binder.

4.4 SCHEDULED AND UNSCHEDULED VISITS

There will be three study visits, including a screening visit. Participants will attend the clinical site for a total of 2.5 hours. Participants will also be asked to complete at home ratings on Day 1, Day 7 and Day 10, to assess their experience with the study CL.

4.4.1 STUDY VISITS

A summary of study visits is shown in Table 2.

Table 2: Summary of visits

Visit #	Day/s	Visits	Duration (hours)
Visit 1	0	Screening and fitting	1.0
Visit 2	0	Baseline & Dispense. Instructions on "at home ratings"	0.5
Given to participant at Visit 2	Day 1, Day 7, Day 10	Subjective at-home ratings	0.5
Visit 3 & Exit	14 (-2/+2) after V2	Day 14 Follow-up	1.0

Visits that fall outside of the specified visit windows will be designated as minor protocol deviations and at the end of the study, the data collected during protocol deviations will be assessed for their suitability to be included in the analysis population.

4.4.2 SCREENING (VISIT 1)

A documented informed consent process will be conducted with all participants prior to their enrolment in the study and prior to any data collection or measurements.

Participants will be assigned a study ID number after they sign the consent documentation process i.e. before their eligibility for the study has been confirmed. The investigator will determine participant eligibility using the inclusion and exclusion criteria. Ineligible participants will be discontinued from the study. The procedures to be performed are outlined below:

Participants will attend this visit having not worn their contact lenses for 12hrs prior to the visit.

1. Informed consent
2. Participant demographics and medical history:
 - *Age, Sex*
 - *Medical history/medications, Allergies*
3. CL wear & digital device use history
 - *Habitual contact lens wear (CL type, cleaning solution (if applicable), wear time and comfortable wear time; Eye drop / artificial tear use (if applicable))*
 - *Digital device use (device kind, combined duration)*
4. Unaided or with habitual spectacles; monocular & binocular logMAR distance high illumination high contrast visual acuity (HIHC VA)
5. Biomicroscopy examination
6. Auto refraction/auto keratometry
7. Sphero-cylindrical refraction, monocular & binocular logMAR distance HIHC VA
8. Best sphere refraction, monocular & binocular logMAR distance HIHC VA
9. Precision1 study lens fitting
 - a. The contact lens power will be chosen based on the vertexed best sphere refraction.
 - b. The participant will insert the lenses.
 - c. Acceptability of lens fit (centration, movement, limbal coverage, overall; YES/NO) will be confirmed.
 - d. Monocular over-refraction will be performed to determine if a different power is needed. If any changes are made, the above procedures will be repeated.
 - e. The final lens powers for OD and OS and monocular & binocular logMAR distance HIHC VA will be recorded.

10. Confirm eligibility.

4.4.3 BASELINE & DISPENSE (VISIT 2)

Participants who successfully met all eligibility criteria will directly transition to Visit 2, while continuing to wear the pair of study lenses that has just been fitted.

1. Subjective post-insertion ratings (0-100 scale, where 100 means better performance; integer steps, both eyes rated together), to assess the first impression of Precision1 regarding:
 - *Comfort;*
 - *Dryness;*
 - *Clarity of vision;*
2. Lens fit & surface assessment
3. Time to haze
4. Lens dispense: Participants will be provided with a supply of Precision1 CLs to last them until their next study visit (12-16 days after V2).
5. At-home rating scales: Participants will receive at home rating scales, to be completed on Day 1, Day 7 and Day 10.
6. Participant instructions. The participants will be asked to:
 - *Wear the lenses at least 5 days per week and 10 hours per day throughout the study;*
 - *To complete subjective ratings at home to reflect their lens wear experience on Day 1 (the day after V2), Day 7 and Day 10 using a 0-100 scale, where 100 means better performance; integer steps, both eyes rated together). Ratings will be completed at lens insertion, after 6 hours of digital device use, and just before CL removal. Variables to be assessed are:*
 - *Comfort*
 - *Dryness*
 - *Clarity of vision*
 - *Attend V3 after 6 hours or more of Precision1 study lens wear;*

4.4.4 DAY 14 FOLLOW-UP & EXIT (VISIT 3)

Participant to attend visit after 6 hours or more of Precision1 study lens wear.

1. Collect unused study CLs;
2. Changes in medical history/medications;
3. Compliance with # of CL wear days/hours per day (total & comfortable) and # hours of digital device use over past 2 weeks and for V3 visit day;
4. Collect and review at-home ratings;
5. Study CL logMAR HIHC VA for OD, OS and OU;
6. Subjective ratings (0-100 scale, where 100 means better performance; integer steps, both eyes rated together), to assess a typical day in the past 2 weeks for insertion, after 6 hours of digital device use, and just before CL removal.
 - *Comfort*
 - *Dryness*
 - *Clarity of vision*
7. Satisfaction (4-point Likert scale: strongly disagree, slightly disagree, slightly agree, strongly agree) with Precision1 CLs overall and when using digital devices on a typical day in the past 2 weeks
8. Lens fit & surface assessment
9. Time to haze
10. Lens removal
11. Biomicroscopy examination

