4.2 STUDY POPULATION

4.2.1 SAMPLE SIZE CALCULATION

The sample size required for a 2-tailed matched paired t-test to detect a change of 5 points in a 0-100 subjective rating scale, with $\alpha=0.05$, power = 0.90, and an effect size of 0.60 is 32 to complete the study, i.e. a minimum sample size of 32 participants completing the study.

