4.2.2 NUMBER OF PARTICIPANTS

Participants will be recruited / screened using CORE records and advertising approved by the UW Office of Research Ethics. Up to 35 participants who meet all eligibility criteria may be dispensed with Precision1 study lenses and asked to wear these lenses for 14 ± 2 days, with a target of 32 completing the study. Participants who were screened but did not meet all eligibility criteria are not included in the number of participants (n=35) to be dispensed. Informed consent will be obtained for all participants prior to their enrolment in the study (Appendix 1).

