10 STATISTICAL ANALYSIS AND DATA MANAGEMENT

10.1 STATISTICAL ANALYSIS

All data will be analyzed by CORE at the University of Waterloo. Data analysis will be conducted using Statistica, SPSS, or other appropriate software.

Descriptive statistics will be provided for all primary outcome variables as well as information regarding baseline variables (e.g. age, sex).

Subjective ratings, lens fit assessments and time to haze will be compared between Visit 2 (Precision1 Dispense) and Visit 3 (2-week follow-up) using either Paired t-tests or Wilcoxon matched pairs, or using ANOVA, as applicable; statistical significance will be set at 5%. The appropriate tests will be selected based on tests of normality - non-parametric tests will be used for data not showing a normal distribution. For assessments conducted for each eye separately, the right eye will be used for analysis if there is no difference between eyes.

Binomial testing will be conducted to analyze Likert questionnaires (strongly agree, slightly agree, slightly disagree, strongly disagree) to determine whether participants had a positive or negative experience with the test lens.

Additional analysis may be conducted.

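### The Visit 2 to Visit 3 test of the insertion ratings in Section 10.1 sets a momentary first impression against a recalled typical day, so change over wear is confounded with rating mode

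*Combined protocol and SAP*

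**What the plan says.** The comparison is set in Section 10.1: "Subjective ratings, lens fit assessments and time to haze will be compared between Visit 2 (Precision1 Dispense) and Visit 3 (2-week follow-up"), by paired t-test, Wilcoxon matched pairs or ANOVA as applicable, and "statistical significance will be set at 5"%.

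Section 4.4.3 describes the Visit 2 rating. It is a post-insertion rating, taken "to assess the first impression of Precision1 regarding" comfort, dryness and clarity of vision, while the participant is still wearing the pair fitted at Visit 1. No 6-hour or end-of-day rating is taken at that visit.

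Section 4.4.4 describes the Visit 3 rating. It uses the same three attributes on the same 0 to 100 scale, but the participant is asked "to assess a typical day in the past 2 weeks for insertion, after 6 hours of digital device use, and just before CL removal". Section 4.5.2 confirms that this is an overall summary of the past two weeks.

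Sections 4.4.3 and 4.5.2 also provide for home ratings on Days 1, 7 and 10, including one made straight after the lenses go in. Section 10.1 does not name these in any comparison.

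**The concern.** A paired test of change assumes that both members of the pair measure the same thing at different times. Here the instruction changes along with the time. The first score describes how the lenses feel now, on first exposure. The second describes how insertion has usually felt over the period, recalled after at least 6 hours of wear that day. A shared scale and shared attributes do not remove that difference.

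These ratings belong to the primary outcome in Section 2, and the sample size in Section 4.2.1 rests on a paired change in a rating of this kind. If the test is significant, the reader cannot tell adaptation or deterioration over two weeks from a difference between momentary and recalled scoring. If it is not significant, a mode effect in the opposite direction may have hidden a real change. No section acknowledges or justifies the change of recall period.

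**Working it through.** **1. Which ratings can be paired.** Section 2 lists three attributes at three times of day, so 3 × 3 = 9 primary ratings. Visit 2 supplies only the post-insertion set, so 3 of the 9 have a Visit 2 counterpart. Section 10.1 does not say which Visit 3 time point is meant. Insertion is the only match; the 6-hour or end-of-day rating would be less comparable still.

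**2. The available insertion ratings side by side.**

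| | Visit 2 | Visit 3 | Home, Days 1, 7 and 10 |
|---|---|---|---|
| What is rated | First impression, at that moment | Typical day over two weeks, recalled | That day's insertion |
| Setting | Clinic, on the pair just fitted | Clinic, after 6 hours or more of wear | Home, straight after insertion |
| Scale | 0 to 100, integer, both eyes together | Same | Same |
| Named in Section 10.1 | Yes | Yes | No |

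The two ratings that are tested differ in what is rated. The home ratings share one mode with each other.

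**3. The plan's own figure.** Section 4.2.1 gives the target as a two-sided paired t-test "to detect a change of 5 points in a 0-100 subjective rating scale", with α = 0.05 and "power = 0.90, and an effect size of 0.60 is 32 to complete the study". With the noncentral t distribution (df = n − 1, noncentrality 0.60 × √n), power is 0.898 at n = 31 and 0.908 at n = 32. The stated 32 is reproduced and is not in dispute.

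**4. Implied spread.** SD of differences = 5 / 0.60 = 8.33 points. This is derived; the protocol does not state it. The standard error at n = 32 is 8.33 / √32 = 1.47 points.

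**5. What a mode shift would do (illustration only).** The documents give no size for the shift, so the values below are assumptions. With no true change, noncentrality = shift / 1.47, and the probability of p < 0.05 is:

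| Assumed shift (points) | Noncentrality | Probability of p < 0.05 |
|---|---|---|
| 0 | 0 | 0.05 |
| 1 | 0.68 | 0.10 |
| 2 | 1.36 | 0.26 |
| 3 | 2.04 | 0.51 |
| 5 | 3.39 | 0.91 |

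In the other direction, a shift of 2 points against a true 5-point change leaves 5 − 2 = 3 points, and power falls from 0.91 to 0.51.

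**The case against.** The strongest reply is that this is an open-label, single-lens pilot. Its objectives are to assess ratings and determine satisfaction, and its hypothesis is satisfactory performance, not change from dispense. Section 10.1 also promises descriptive statistics for all primary outcomes. For that purpose a two-week typical-day rating is a sensible item, and blending early with late wear is what such a summary is meant to do. This stands: the Visit 3 item is not at fault. It does not rescue the comparison, because Section 4.2.1 powers a paired test and Section 10.1 specifies one at the 5% level.

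It could also be said that the ANOVA option leaves room for the home ratings. As written, that option sits within the Visit 2 versus Visit 3 comparison.

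The rejection probabilities are the planned test's power curve at assumed shifts. They show what a bias of a given size would do, not that one is present. That limitation is accepted.

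A reader might infer further sources of bias that the documents do not support:

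- **Review of home ratings before the Visit 3 ratings.** Table 3 describes this as a check of compliance and completion. Nothing says that participants re-read or discuss their scores.
- **An end-of-wear state at Visit 3.** Six hours is a minimum, against a wearing day of at least 10 hours, so the visit may fall mid-wear.
- **A long delay before the Visit 2 rating, made longer by a power change.** Visit 1 lasts 1.0 hour in all, insertion comes late in it, and a changed lens is newly inserted.

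**Conclusion.** The concern holds for one comparison: the Visit 2 to Visit 3 test of the three insertion ratings. Followed as written, it confounds change over wear with rating mode, and no other section cures this. Lens fit and time to haze are measured directly at both visits and are unaffected.

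It would go too far to say that the result carries no information about change, or that it is biased in a known direction. The supportable statement is that a difference cannot be attributed to two weeks of wear alone. Its size is unknown. The 26% and 51% for assumed shifts of 2 and 3 points rest on the implied SD of 8.33, 32 completers and use of the paired t-test, where Section 10.1 also allows Wilcoxon. The point should be corrected, but it does not undermine the descriptive aims of the study.

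**What to change.** In Section 10.1, take the insertion ratings out of the Visit 2 versus Visit 3 test. Test change in insertion comfort, dryness and clarity on the home ratings made straight after insertion, Day 1 versus Day 10, with Day 7 as an intermediate point. Report the Visit 2 first-impression and Visit 3 typical-day ratings descriptively, labelled as different kinds of rating. State the SD of differences assumed for the chosen pair; the sample size formula does not change.

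The Visit 3 questionnaire and the order of procedures can stay as they are. A home insertion rating on the morning of Visit 3 is an optional addition that would restore a Day 14 end point.

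The cost is small, because the data are already planned. There are three drawbacks:

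- Unsupervised home ratings may have somewhat more missing data, and with wear required on only 5 days a week a rating day may fall on a day without lenses.
- The start point becomes Day 1 instead of first exposure.
- The end point becomes Day 10 instead of Day 14, unless the optional rating is added.

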4.4.5 STUDY EXIT

The study exit form will be completed when a participant exits the study. This form will be completed either at study completion, or if the participant is discontinued from the study at another time. A study exit form must be completed for all participants who have taken a study ID number. If in the opinion of the investigator post-study follow-up visits are required, the exit form will be completed after the last follow-up visit.

Exit monocular and binocular distance (HIHC VA logMAR) will be recorded with either the participant's spectacles, refraction or habitual contact lenses. An exit biomicroscopy assessment will be conducted if not already completed on the same day for a concurrent study visit.

After the exit assessments have been completed, the participant and investigator will complete the study completion and remuneration forms. At this time the participant will be considered as having exited the study.

4.4.6 UNSCHEDULED VISITS

An unscheduled visit is defined as an interim visit requested by the participant or investigator due to an unanticipated problem. Data recorded at these visits will be entered into the database. Only relevant and applicable unscheduled visit information will be included in the final report as deemed necessary by the lead investigator.

4.5 STUDY PROCEDURES

Table 3 summarizes the procedures at each visit. The order of procedures is described in sections 4.4.2 to 4.4.4.

Table 3: Summary of procedures to be conducted at scheduled visits

Procedure	Visit 1	Visit 2	Visit 3
	Screening	Baseline & Dispense	Day 14 Follow-up
Informed consent	X		
Participant demographics (age, sex)	X		
Medical history and medications	X		
Changes in medical history/ medications			X
Contact lens history	X		
Digital device use history	X		
HIHC VA (logMAR) (unaided or with habitual spectacles)	X		
Biomicroscopy	X		X
Auto refraction/auto keratometry: horizontal and vertical K readings	X		
Subjective refraction	X		
HIHC VA (logMAR) (study CL)	X		X

Study lens fitting	X		
Eligibility	X		
Subjective ratings (Post-insertion re Comfort, Dryness & Vision)		X	
Lens performance (fit, wettability, pre-lens TBUT, deposition)		X	X
Time to haze		X	X
Study lens dispense		X	
Subjective at-home ratings (Comfort, Dryness & Vision) provided		X	
Review of compliance (CL wear, digital device use, completion of home ratings)			X
Subjective ratings (Comfort, Dryness & Vision)			X
Satisfaction ratings (Likert scale for agreement)			X
Collection of unused study lenses			X
Study Exit			X

4.5.1 CASE HISTORY

Demographics:

Demographic information from the participant will be obtained, including age and sex.

Medical History:

At screening, information will be obtained from participants about the current medication, allergies, and any medical conditions. At visit 3 participants will be asked about changes in their medication or health.

Contact Lens History:

Information will be obtained from the participant about the current contact lens type (lens name, brand), lens power, lens wear days and use of artificial tears. Participants will be asked their typical total wear time (hours/day) and comfortable wear time (hours/day).

Digital device use:

Participants will be asked about their typical use of digital devices (total hours/day of all devices combined), and to identify the kind of devices (e.g. smartphone, computer, laptop, tablet) they use.

4.5.2 SUBJECTIVE RATINGS

Subjective ratings:

At visit 2, participants will be provided with subjective rating 0-100 questionnaires to assess their first impression with the study CLs post insertion regarding comfort, dryness and clarity of vision.

At the end of visit 2, they will be provided with at-home questionnaires to subjectively rate the experience with the study lenses regarding comfort, dryness and clarity of vision using a 0-100 scale (integer steps; both eyes together), where 100 means better performance. This questionnaire will be completed at home on Days 1, 7 and 10 after Visit 2 (i.e. Day 0), at three different time-points on each of these days: directly after insertion, after 6 hours of digital device use, and at the end of day just before lens removal. In addition, times of lens insertion, first notice of discomfort, and lens removal will be collected.

The same questionnaire will be provided to the participants during V3 to assess their overall 'typical day' experience during the past 2 weeks.

Satisfaction with study CL:

Satisfaction (4-point Likert scale: strongly disagree, slightly disagree, slightly agree, strongly agree) with Precision1 CLs overall and while using digital devices on a typical day in the past 2 weeks will be assessed for the following questions:

- *The study lenses provide good vision all day long;*
- *The study lenses provide good comfort all day long;*
- *I am satisfied with the comfort the study lenses provide when I use digital devices for ≥ 6 hours;*
- *I am satisfied with the vision the study lenses provide when I use digital devices for ≥ 6 hours;*
- *I don't experience eye strain when I wear the study lenses and use digital devices for ≥ 6 hours.*
- *I don't experience eye fatigue (tired eyes) when I wear the study lenses and use digital devices for ≥ 6 hours.*
- *I don't experience episodes of blurred vision when I wear the study lenses and use digital devices for ≥ 6 hours.*

- Overall, these lenses provide good performance when using digital devices for ≥ 6 hours.

4.5.3 VISUAL ACUITY

Visual acuity for distance will be measured using high contrast computer-generated acuity charts in high illumination. Participants will be asked to read letters that progressively decrease in size on a computer screen located at a distance of 6 meters.

4.5.4 AUTOREFRACTION

Participants will be asked to focus on a target while seated at an instrument that measures their approximate spectacle prescription and corneal shape.

4.5.5 SUBJECTIVE REFRACTION

Participants will be asked to read a letter chart from a distance through lenses placed in front of their eyes. They will also be asked to compare clarity of their vision between different lenses placed in front of their eyes. This procedure aids to determine their spectacle and/or contact lens prescription.

4.5.6 SLIT LAMP BIOMICROSCOPY

The participant will be seated behind a slit lamp and the following may be assessed at any visit:

External adnexa anomalies:

Any current observations of the anterior eye (e.g. pterygium, pinguecula, etc) will be recorded.

Cornea:

Any current or past corneal observations (such as infiltrates, old scars, etc) will be documented.

Conjunctival redness:

Ocular redness will be assessed for the bulbar and limbal conjunctiva using the EFRON grading scale (0 to 4, 0 = normal; 0.1 increments).

Corneal and conjunctival staining with fluorescein:

Corneal staining will be assessed for 5 zones, by grading type (0-4, 0.5 steps), extent (0-4, 0.5 steps) and depth (0-4, integer steps);

Lens edge related conjunctival staining and conjunctival indentation will be assessed for 4 zones (0-4, 0.5 steps);

Palpebral conjunctival hyperemia and roughness:

The redness and roughness of the upper and lower eyelids (tarsal plate zone 2) will be assessed using the Efron grading scale (0 to 4, 0 = normal/ uniform satin appearance; 0.25 steps).

4.5.7 LENS FIT & SURFACE ASSESSMENT

Contact lens fit:

Lens fit will be assessed to ensure acceptable lens fit with study lenses at the screening visit.

At V2 and V3, lens centration and movement will be assessed as follows

- *Lens centration (scale: optimal, slight decentration, moderate decentration but not encroaching limbus, excessive & occasionally encroaching limbus);*
- *Lens movement for primary gaze (-2 = Unacceptably tight; -1 = Slightly tight but acceptable; 0 = Optimal; +1 = Slightly loose but acceptable; +2 = Unacceptably loose); lens tightness on push-up test (0-100 scale, with 50 being optimal; 5-point steps);*

Contact lens wettability, pre-lens tear break-up time and deposits:

Contact lens wettability and deposits will be graded with study lenses at V2 and V3:

- *Surface wettability (0-4 scale in 0.25 steps; 0 being excellent);*
- *Pre-lens tear break up time (TBUT), average of 3 measures (seconds)*
- *Surface deposits (0-4 scale in 0.25 steps; 0 being excellent);*

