1 INTRODUCTION

Approximately 22% of new contact lens (CL) wearers cease contact lens wear within the first year, with handling (25%), poor distance (23%) and/or near vision (21%) and discomfort (21%) being the main reasons for discontinuation.¹ With today's ever-expanding access to digital devices, the number of potential CL wear drop-outs may further be affected by digital device use. A recent review found a higher prevalence of symptoms of eye strain, eye fatigue or blurred vision in CL wearers compared to non-CL wearers (65% vs 50%) when using digital devices.² The symptoms associated with digital device use in contact lens wear may be affected by multiple factors, including an insufficient blink rate or a poorly wetting contact lens.

Time to haze (TTH) is a metric that has been developed at CORE to measure the maximum time a contact lens wearer can keep their eye open without their vision becoming hazy (conducted just above contrast threshold level); it is a measure of how the drying of the CL surface with open eyes affects vision.

Alcon has recently introduced a new silicone hydrogel (SiHy) daily disposable contact lens (DD CL), called Precision1, which is manufactured from the verofilcon A material. Precision1 DD CLs use 'SMARTSURFACE Technology; which Alcon describe as "*a permanent, micro-thin, high-performance layer of moisture at the lens surface that helps support a stable tear film to deliver lasting visual performance from morning to night*".³

The purpose of this study is to evaluate the performance of Precision1 DD CLs with regard to subjective symptoms (dryness, comfort, vision), lens fit and time to haze in CL wearers who identify themselves as heavy digital devices users (at least 6 hours of digital device use per day).

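### Lens movement and push-up tightness are best at mid-scale, so the planned Visit 2 to Visit 3 tests on unrecoded scores measure a net tight/loose shift, not whether fit improved or worsened

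*Combined protocol and SAP*

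**What the plan says.** Section 4.5.7 defines three fit grades recorded at both Visit 2 and Visit 3.

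- **Movement in primary gaze** is a five-grade score from -2 (unacceptably tight) to +2 (unacceptably loose). Its upper half reads "0 = Optimal; +1 = Slightly loose but acceptable; +2 = Unacceptably loose".
- **Push-up** is recorded as "lens tightness on push-up test (0-100 scale, with 50 being optimal; 5-point steps").
- **Centration** runs one way, from optimal to excessive decentration.

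Section 10.1 states: "Subjective ratings, lens fit assessments and time to haze will be compared between Visit 2 (Precision1 Dispense) and Visit 3". The method is "using either Paired t-tests or Wilcoxon matched pairs, or using ANOVA, as applicable", chosen by a normality check, at the 5% level. The section does not say that movement or push-up will be re-expressed as distance from the optimum, and it specifies no table of fit categories by visit. Descriptive statistics are promised for the primary outcomes and baseline variables only. The section also leaves room for further, unspecified analyses.

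Lens fit is listed in section 2 among the other outcomes. The Introduction includes it in what the study sets out to evaluate: "subjective symptoms (dryness, comfort, vision), lens fit and time to haze". At screening (section 4.4.2), "Acceptability of lens fit (centration, movement, limbal coverage, overall; YES/NO) will be confirmed", so only acceptable fits enter.

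**The concern.** A paired test works on the signed difference, Visit 3 minus Visit 2. That suits a scale on which one end is good and the other bad. On a scale with its optimum in the middle, the signed difference measures direction (tighter or looser), not quality.

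Two errors of reading follow. First, if some lenses tighten and others loosen, the differences offset each other and a real loss of fit can be reported as no change. Second, a significant result is ambiguous: a move from +1 to 0 improves fit and a move from 0 to -1 worsens it, yet both contribute -1.

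With no table of fit grades planned, nothing in the specified output would reveal either problem.

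**Working it through.** **The plan's own figure.** Section 4.2.1 gives 32 completers for a two-sided paired t-test with effect size 0.60, alpha 0.05 and power 0.90. The noncentral t distribution gives power 0.898 at n = 31 and 0.908 at n = 32, so 32 is reproduced. It was set for the 0-100 subjective ratings and does not depend on this point. It is used below only as the number of participants.

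**Inputs.** The scales come from section 4.5.7, the tests and the 5% level from section 10.1, and n = 32 from section 4.2.1. The documents give no expected fit grades, so all counts and standard deviations below are assumptions.

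**1. Cancellation (movement).** Assume 16 of 32 participants move one grade away from optimal and 16 do not change. Let *a* move one way and *b* the other, with a + b = 16. For the signed changes:

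- mean = (a - b)/32
- variance = (16 - 32 × mean²)/31
- t = mean / (SD/√32), on 31 degrees of freedom

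Example, 12/4: mean = 8/32 = 0.25; variance = (16 - 2)/31 = 0.4516; SD = 0.672; t = 0.25/(0.672/5.657) = 2.10; p = 0.044.

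The exact rank test drops the 16 zeros. The remaining changes all have equal rank, so it reduces to a binomial test of *a* out of 16.

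| Direction split | Signed paired t, p | Signed exact rank test, p | Distance from optimal, t / exact p |
|---|---|---|---|
| 8/8 | 1.00 | 1.00 | 4e-6 / 3e-5 |
| 10/6 | 0.33 | 0.45 | 4e-6 / 3e-5 |
| 11/5 | 0.14 | 0.21 | 4e-6 / 3e-5 |
| 12/4 | 0.044 | 0.077 | 4e-6 / 3e-5 |
| 13/3 | 0.010 | 0.021 | 4e-6 / 3e-5 |
| 16/0 | 4e-6 | 3e-5 | 4e-6 / 3e-5 |

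The loss of fit is the same in every row. The signed t-test first reaches 5% at 12 of 16 movers in one direction (75%). The large-sample Wilcoxon agrees (p = 0.046 at 12/4). The exact rank test needs 13 of 16 (81%).

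**2. Ambiguity.** If 16 of 32 shift by -1 and the rest do not change, the signed t-test gives p = 4e-6 whether they went from +1 to 0 (better) or from 0 to -1 (worse).

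**3. Push-up, by simulation.** Scores were assumed normal, rounded to 5-point steps, n = 32, independent between visits, 5,000 runs.

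| Assumed change, Visit 2 to Visit 3 | Signed t rejects | Distance-from-50 t rejects |
|---|---|---|
| Mean 50 throughout, SD rises from 5 to 10 (fit worsens both ways) | 5% | 89% |
| Mean moves from 45 to 55, SD 5 (no change in distance from optimal) | 100% | 5% |

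In the first case the signed test rejects only at its error rate. In the second it is almost certain to be significant although fit is no further from optimal.

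**4. Behaviour of the distance test.** With no true change and the same SD (5 to 10) at both visits, 4,000 runs gave rejection rates of about 5%. The floor matters when Visit 2 grades sit at optimal. If all 32 were graded 0, any re-grading counts as worse: six such changes give an exact p of 2 × 0.5⁶ = 0.031, and five give 0.063.

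**The case against.** The strongest reply has five parts.

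- **Silence is not a decision.** Section 10.1 does not say which form of the fit score is compared, and an analyst might recode. That is true. But as written the tests apply to the recorded scores, and choosing the scoring after seeing the data is avoidable.
- **The illustration favours the point.** Every mover is assumed to leave optimal, and the counts are invented. All participants wear one lens design, Visit 2 directly follows fitting and Visit 3 follows at least six hours of wear, so a common-direction drift is plausible. This stands as a limit: the signed test would detect such a drift, though the p-value alone would still not say whether fit improved.
- **Entry requires an acceptable fit**, which narrows the Visit 2 range. But acceptable movement includes -1, 0 and +1, so both sides of the optimum remain open.
- **The distance test has weaknesses of its own.** It is blind to a crossing from 45 to 55. If all lenses start at optimal, random one-grade re-grading of 15% or 20% of them at Visit 3 gives an exact p below 0.05 in about 35% or 64% of trials (the chance of six or more out of 32). This also stands, and is why the signed scores and a table must accompany the test.
- **Fit is a secondary matter** in an open-label, single-arm pilot, absent from the objectives and hypothesis. That caps the importance of the point but does not remove it, because section 10.1 commits to a significance test on fit.

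**Conclusion.** The concern holds. For movement and push-up, the analysis as written answers whether lenses became tighter or looser on balance, not whether they fitted better or worse. Under the assumed 16 movers out of 32, a mixed-direction loss of fit goes undetected until about 75% of movers go the same way (81% with the exact rank test). A significant result cannot, from the test alone, be read as improvement or deterioration.

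The size depends on the assumed counts and on how mixed the directions are; a mostly one-directional change would be found. Centration, the primary ratings and the sample size are not affected. This should be corrected before analysis, but it does not threaten the main result.

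**What to change.** In section 10.1, for these two scores only:

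1. Compare |movement| and |push-up - 50| between Visit 2 and Visit 3 as the measure of fit quality.
2. Keep the signed scores as a description of direction.
3. Tabulate tight/optimal/loose at each visit and, for movement, the proportion graded -1 to +1. State which end of the push-up scale is tight, since section 4.5.7 does not.
4. If both eyes are ever averaged, take the distance within each eye first; otherwise +1 and -1 cancel again. Section 10.1 uses the right eye when the eyes do not differ and does not say what happens when they do.
5. State that distance has a floor at 0, so lenses graded optimal at Visit 2 can only stay the same or worsen, and read the test together with the table.

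The cost is a few sentences of analysis text and the matching code, with no new data, visits or participants. The remaining cost is interpretive: the floor effect in item 5.
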